7.4 Variables

7.4.1 Context and rationale for exposures of interest

Operational definitions for the two treatment strategies that will be compared are presented in [Table 6](#). Exposure will be defined based on treatment initiated during the 15-day exposure ascertainment window. While patients in the PALOMA-2 trial received study treatments on the same day, a 15-day window was selected to allow for potential delays in data entry and treatment administration variability that may occur in routine practice. In a feasibility assessment of 944 patients in the data source who initiated both letrozole and palbociclib as first-line therapy, 93.3% started both medications within 15 days. A shorter exposure window may be too restrictive and result in few eligible patients, while longer time periods may result in treatment patterns in the study population that are vastly different from the trial. As discussed above, patients who experience a censoring event or death during the exposure ascertainment window will be excluded from the study to align the start of follow-up for both exposure groups.

Table 6. Operational Definitions of Exposures

Group name(s)	Details	Washout window	Assessment Window	Incident with respect to...	Source of algorithm	Validity concerns and how they will be addressed
Exposed	Patients initiating treatment with palbociclib and letrozole within 15 days of one another, in the metastatic setting	N/A, treatment in first-line metastatic setting	[Metastatic diagnosis date, Day -1]	Metastatic Diagnosis	Curated regimen definition; clinical experts	Real-world exposure group definitions allow for more flexibility in treatment timing than in the trial. The potential impact of this on results will be explored through a sensitivity analysis shortening the duration of the exposure ascertainment window (Table 11).
Comparator	Patients initiating treatment with letrozole with no evidence of palbociclib treatment within 15 days, in the metastatic setting	N/A, treatment in first-line metastatic setting	[Metastatic diagnosis date, Day -1]	Metastatic Diagnosis	Curated regimen definition; clinical experts	

N/A = not applicable

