7.4.3 Context and rationale for follow-up

Follow-up will begin on Day 0, and will continue until the earliest of:

1. Date of documented progression or death ([Table 7](#));
2. Initiation of any new anti-cancer therapy;
3. The administrative end of the study period (Day 1004, or 33 months, of follow-up), to align with the maximum follow-up time at which PFS was evaluated in the PALOMA-2 trial;
4. End of the data (July 20, 2023);
5. Loss to follow-up: The last date of curated EHR activity prior to a period of >90 days without curated EHR activity and without death.

Operational definitions for the study censoring criteria are presented in [Table 8](#). These censoring criteria correspond to those applied in the PALOMA-2 RCT where applicable.

Table 8. Operational Definitions of Censoring Criteria

Trial Criterion	Real-world operationalization	Rationale for real-world operationalization (where applicable)	Validity concerns and how they will be addressed (where applicable)
Initiation of a new anti-cancer treatment	Treatment with any new anti-cancer therapy.	N/A	N/A

Trial Criterion	Real-world operationalization	Rationale for real-world operationalization (where applicable)	Validity concerns and how they will be addressed (where applicable)
End of study	Administrative end of study (Day 1004, or 33 months) or July 20, 2023.	Align with maximum time in PALOMA-2 or end of available data in real-world data source.	N/A
Withdrawal of consent	This criterion is not relevant in a real-world clinical setting.	N/A	N/A
Loss to follow-up	A period of >90 days without curated EHR activity and without death.	Curated activity in the real-world data source indicates points at which progression can be recorded. Metastatic breast cancer patients likely have contact with the healthcare system at least every 90 days for lab work, prescription refills, outpatient visits, or scans. Periods greater than 90 days may indicate loss to follow-up during which censoring or outcome events cannot be captured.	Patients who use the health care system less frequently will be censored. A sensitivity analysis will be conducted expanding the period without curated activity to >180 days (Table II).

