7.5 Data analysis

7.5.1 Context and rationale for analysis plan

Analytic Population

Primary analyses will be conducted in the real-world study population based on the first study treatment initiated. This approach is intended to emulate the intent-to-treat analysis conducted in the PALOMA-2 trial, where patients were analyzed based on their randomized treatment assignment. As crossover between treatment arms was not allowed in the PALOMA-2 trial, intent-to-treat and per-protocol trial analyses would produce equivalent results. Conversely, real-world patients initially prescribed letrozole could initiate palbociclib after the end of the exposure ascertainment window. To investigate the potential for crossover between comparison groups prior to disease progression in the real-world population, descriptive analyses of all first-line treatments initiated and time between treatments will be conducted.

IPTW will be used to approximate full conditional exchangeability between the comparison groups and facilitate estimation of the population average treatment effect.¹⁶⁻¹⁸ Propensity scores (PS) reflecting the conditional probability of initiating treatment with palbociclib and letrozole will be calculated via multivariable logistic regression. Exposure to palbociclib and letrozole will be regressed on *a priori* identified potential confounders ([Table 9](#)). Inverse probability of treatment weights will be calculated as the inverse of the propensity score (1/PS) for patients in the exposed group and as the inverse of one minus the propensity score (1/1-PS) for comparator patients.¹⁹ Patients are therefore weighted by the inverse probability of initiating the treatment they actually started, conditional on the observed covariates included as independent variables in the PS model. This approach aims to create a pseudo-population with full exchangeability on measured confounders within which the treatment effect is estimated.

Confounder balance will be assessed by comparing the absolute standardized difference (ASD) in the distribution of categorical variable levels and the mean of continuous variables between the weighted exposure groups.¹⁶ If balance is not achieved (ASD > 0.1), alternative specifications of the PS model, e.g., including variable transformations and interaction terms, will be explored. Confounders with insufficient balance may also be included as covariates in the outcome models.

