Modified exposure ascertainment window (one day)	Exposure status is ascertained over a 15-day window following first study drug initiation.	The exposure ascertainment window will be shortened to occur over a single day.	Shortening the exposure ascertainment window will exclude patients who initiate letrozole and palbociclib greater than 1 day apart from the exposed group.	This analysis will more closely align the treatment strategy in the exposed group to that of the trial.	Patients who initiate palbociclib greater than 1 day after letrozole will be eligible for inclusion in the comparator group, which may bias results towards the null.
Modified exposure ascertainment window (30 days)	Exposure status is ascertained over a 15-day window following first study drug initiation.	The exposure ascertainment window will be increased to occur over 30 days.	Increasing the exposure ascertainment window will include patients who initiate letrozole and palbociclib greater than 15 days apart in the exposed group.	This analysis will increase follow-up time for patients who initiate study drugs further apart in time and will employ a more flexible definition of the exposure ascertainment period that aligns with the data vendor line of therapy definition.	Patients who initiate palbociclib greater than 15 days after letrozole will be eligible for inclusion in the exposed group, which may less accurately reflect the treatment strategy used in the trial.

Description	Primary Analysis	Sensitivity Analysis	Rationale	Strengths of the sensitivity analysis compared to the primary	Limitations of the sensitivity analysis compared to the primary
Loss to follow-up censoring definition	Patients are censored on the last date prior to a period of >90 days without curated EHR activity and without death.	Censor patients on the last date prior to a period of >180 days without curated EHR activity and without death.	Lengthening the time period without curated EHR activity will allow patients who are using healthcare less frequently to have outcomes recorded after a gap in 180 days of activity.	Progression and death events that occur after a gap of 90 days without curated EHR activity will be included.	Lengthening the time period without curated EHR activity will increase the possibility of unobserved events or censoring reasons and potentially overestimate rwPFS.

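### The one-day exposure-window sensitivity analysis changes the comparator group and Time 0 as well as the exposed group, so a shift in its hazard ratio cannot be attributed to the exposed-group definition alone

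*Combined protocol and SAP*

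**What the plan says.** Section 7.4.1 classifies patients over a 15-day window that starts at the first study drug. Section 7.3.1 places Time 0 on the day after that window ends. For the exposed group, Table 6 notes that "Real-world exposure group definitions allow for more flexibility in treatment timing than in the trial" and names a shorter window in Table 11 as the check on this.

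In that row of Table 11 (Section 7.5.2), "The exposure ascertainment window will be shortened to occur over a single day". The stated strength is that "This analysis will more closely align the treatment strategy in the exposed group to that of the trial". The limitations cell adds that patients who start palbociclib more than a day after letrozole "will be eligible for inclusion in the comparator group, which may bias results towards the null".

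On follow-up, the list in Section 7.4.3 ends observation at "Initiation of any new anti-cancer therapy", and Table 8 operationalizes this as "Treatment with any new anti-cancer therapy". Neither exempts palbociclib. Section 7.5.1 says "Primary analyses will be conducted in the real-world study population based on the first study treatment initiated", accepts that letrozole patients may start palbociclib after the window, and plans descriptive analyses of that crossover.

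**The concern.** The row is there to answer one question: does it matter that real-world combination patients may start the two drugs some days apart? To answer it, the exposed group should change and everything else should stay fixed. Instead three things change together:

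- the exposed group loses its later second-drug starters;
- the comparator group gains those of them who began with letrozole;
- Time 0 moves about two weeks earlier for everyone.

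The plan also leaves open what happens to the moved patients after Time 0. If they stay in follow-up, comparator person-time includes palbociclib treatment. If they are censored at palbociclib start, they enter the propensity model and the balance check and then leave almost at once. The bias statement in Table 11 fits only the first case.

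Section 5 judges the emulation on whether it agrees with the trial in direction and is of similar magnitude. A drift in the HR caused by regrouping patients could be misread as sensitivity to treatment timing.

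**Working it through.** **Plan's own figure.** The plan gives no figure for the one-day analysis. The nearest is the Table 13 floor (HR 0.58, 80% power, two-sided 5%, 1:1, event prevalence 57.7%). Events = (1.960 + 0.842)² / (0.25 × ln(0.58)²) = 7.849 / 0.0742 = 105.8. Divided by 0.577 this is 183.4, so 184, as stated.

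**Inputs from the plan.**
- 944 combination and 660 letrozole-only patients (Section 7.9).
- 93.3% of the 944 start both drugs within 15 days (Section 7.4.1): 0.933 × 944 ≈ 881, leaving 63 outside.
- HR 0.58 and 57.7% comparator events (Table 13); 33-month horizon (Section 7.4.3); trial median follow-up of 23 months (Appendix B).

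**Assumptions, not in the plan.**
- 10%, 20% or 40% of the 881 start more than a day apart, all letrozole-first.
- The 63 are also letrozole-first, so they are already comparators in the primary analysis: 660 + 63 = 723, of whom 63/723 = 8.7% start palbociclib later.
- Hazards are exponential. Moved patients carry the comparator hazard for 7 days and 0.58 times it afterwards; the 63 switch at day 30.
- The comparator hazard per month is −ln(1 − 0.577)/33 = 0.0261, −ln(1 − 0.577)/23 = 0.0374, or ln(2)/12 = 0.0578, giving medians of 26.6, 18.5 and 12 months.
- No weighting is applied.

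**Patients moved.** Moved = 881 × m. Share of the enlarged comparator group = 881m / (723 + 881m).

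**Expected HR.** The large-sample Cox estimate solves the score equation: exposed events = Σ over t of all events(t) × e^β S₁(t) / [e^β S₁(t) + S₀(t)], where S₁ and S₀ are the numbers at risk in the exposed and comparator groups. It was solved with and without censoring at palbociclib start. Without censoring, the primary 15-day analysis gives 0.605 to 0.608 across the three hazards; with censoring it gives 0.580.

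| m | Moved | Comparator group | Moved share | HR, not censored | HR, censored (non-informative) | Moved patients' share of comparator person-time if censored, at most 14 days each |
|---|---|---|---|---|---|---|
| 10% | 88 | 811 | 10.9% | 0.635–0.643 | 0.580 | 0.3–0.4% |
| 20% | 176 | 899 | 19.6% | 0.662–0.672 | 0.580 | 0.6–0.8% |
| 40% | 352 | 1,075 | 32.7% | 0.704–0.717 | 0.580 | 1.1–1.6% |

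**Which censoring rule does Table 11 assume?** The one-day row expects bias towards the null, which needs late palbociclib starters to remain under observation. The 30-day row claims more follow-up for patients who start the drugs further apart. A longer window delays Time 0, so follow-up can grow only if those patients are cut short in the primary analysis. This is an inference, but on that reading the two rows rest on opposite rules.

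**The case against.** The strongest reply is that the plan discloses the effect. Its limitations cell names the patients, their destination and the expected direction of bias. Section 7.5.1 plans descriptions of time between treatments, Section 8 commits to reporting crossover, and a 30-day row probes the other direction. Table 6 promised a shorter window, and Table 11 delivers one; moving Time 0 earlier is a legitimate question in itself. All of that stands. But disclosure does not make the result attributable, and a one-row change would.

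A reader might infer that the analysis contaminates the controls instead of testing the exposure definition, and that its bias statement contradicts Table 8. The documents do not support this as a whole. The row does tighten the exposed group. Dilution and conflict with Table 8 are also alternatives: if the moved patients are censored there is almost no dilution, and if they are not, the stated direction is right. Section 7.5.1 can be read as not censoring crossover, so this is an unresolved conflict between passages and not an established contradiction.

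A reader might also apply the assumed shares to all 944 patients and measure the change from 0.58. That counts about 63 patients who are already outside the 15-day window. It also ignores that, without censoring, the primary HR is itself already diluted to about 0.61.

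**Conclusion.** The concern holds in a limited form. The one-day analysis alters the exposed group, the comparator group and Time 0 together, so its HR cannot isolate the effect of the exposed-group definition.

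If late palbociclib starters stay in follow-up, the HR rises by roughly 0.03, 0.06 or 0.10 from a primary value of about 0.61, for assumed shares of 10%, 20% or 40%. If they are censored non-informatively, the HR stays near 0.58 and the stated bias largely does not arise. What remains is that patients balanced at baseline leave within about two weeks, possibly informatively, with a bias whose direction is not fixed.

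These sizes rest on the assumed shares, the letrozole-first order, exponential hazards, the switch times and feasibility counts taken before the remaining criteria. The problem specific to this row does not alter the primary estimate. The censoring question does reach the primary comparator group, on a smaller scale (63 of 723 under the same assumption).

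**What to change.** Rewrite the one-day row of Table 11:

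- Keep the 15-day window, Time 0 and comparator definition of the primary analysis.
- Restrict the exposed group to patients whose first palbociclib and letrozole records fall on the same day.
- Leave out of both groups anyone who starts the second drug later in the window, whichever drug came first. This also settles patients exactly one day apart and palbociclib-first patients, whom the present row does not clearly place.
- Replace the bias sentence accordingly.

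Because Time 0 still follows day 15, the exclusion uses only information from before Time 0 and adds no immortal time. Dropping these patients while starting follow-up after one day would not have that property.

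Separately, reconcile Section 7.4.3 with Table 8, Section 7.5.1 and Table 11 on whether palbociclib started after the window by a comparator patient is a censoring event.

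The cost is one table row and one clarifying sentence. The exposed group falls to about 793, 705 or 529 (881 less 88, 176 or 352) against 723 comparators, before the remaining criteria and well above the floor of 184 in total. The row would no longer test window length or the placement of Time 0; if those matter, the present version can be kept as a separately labelled analysis.

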7.1 Study design

7.1.1 Overview of key design elements of the PALOMA-2 trial

Study design: The PALOMA-2 trial (NCT01740427)¹¹ was an international, randomized, double-blind, placebo-controlled Phase III clinical trial comparing the efficacy and safety of palbociclib and letrozole versus placebo and letrozole for the first-line treatment of ER+/HER2- advanced breast cancer. [Figure 1](#) displays the study design diagram for the PALOMA-2 trial.

Population: The trial study population included postmenopausal females, 18 years of age or older with histologically or cytologically confirmed ER+/HER2- adenocarcinoma of the breast and evidence of locoregionally recurrent or metastatic disease. Eligible patients had received no prior systemic therapy for advanced disease; did not have disease recurrence during or within 12 months of neoadjuvant or adjuvant treatment with a non-steroidal aromatase inhibitor; had adequate organ function; had an Eastern Cooperative Oncology Group (ECOG) performance status of 0 to 2; and had measurable disease according to the Response Evaluation Criteria in Solid Tumours (RECIST) v.1.1.¹² Patients with visceral metastasis who were at risk of short-term, life-threatening complications were excluded. Full inclusion and exclusion criteria are listed in [Table 4](#) and [Table 5](#).

Endpoints: The primary trial endpoint was progression-free survival (PFS), defined as the time from the date of randomization to the date of the first documentation of objective progression of disease as evaluated by study investigators according to RECIST v.1.1, or death due to any cause. Follow-up for PFS continued until the first of: documented disease progression; death; initiation of a new anti-cancer treatment; discontinuation from overall study participation due to symptomatic deterioration, unacceptable toxicity, withdrawal of consent; or loss to follow-up. Comparator patients were not able to initiate palbociclib.

Analysis: Efficacy was assessed in the intent-to-treat population defined by randomized treatment assignment. Median PFS and corresponding 95% confidence intervals were estimated after a maximum follow-up of 33 months using the Kaplan-Meier method and compared by treatment status using a log-rank test. The hazard ratio for progression was calculated using a Cox proportional-hazards model.

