ECOG performance status 0-2	ECOG performance status 0-2 or missing Karnofsky performance status ≥50 or missing For patients with multiple performance status records, the entry closest in time to study drug initiation will be used.	[Day -105, Day -15]	Performance status will be evaluated in the 90 days before study drug initiation to balance missingness and misclassification, given infrequent real-world assessments.	Patients with missing performance status records who would have been ineligible for the trial may be included. This may affect comparability between the study and trial populations. Sensitivity analyses restricting to patients with known values will be performed, sample size permitting.

Trial Criterion	Real-world operationalization ^a	Assessment window	Rationale for real-world operationalization (where applicable)	Validity concerns and how they will be addressed (where applicable)
Adequate organ and marrow function	No lab results indicating inadequate organ or marrow function as defined in the PALOMA-2 trial protocol.	[Day -45, Day -15]	Lab tests specified in the trial are not performed for all patients in routine oncology care. As a result, patients with lab results indicative of inadequate organ or marrow function will be excluded. Lab results will be evaluated in the 30 days before study drug initiation to balance missingness and misclassification.	Patients with inadequate organ and marrow function and therefore potentially reduced survival who would have been ineligible for the trial may be included. We do not expect this to affect a large number of patients as physicians are unlikely to start treatment for patients with poor organ or marrow function.
Resolution of all acute toxic effects of prior anti-cancer therapy or surgical procedures to National Cancer Institute (NCI) Common Terminology Criteria for Adverse Events (CTCAE) version 4.0 Grade \leq 1	This criterion cannot be operationalized.	N/A	Acute toxic effects and their resolution cannot be identified in the data source.	Patients with ongoing acute toxic effects who would have been ineligible for the trial may be included. We do not expect this to affect a large number of patients as physicians are unlikely to start a new treatment for patients with ongoing acute toxic effects.
Willingness and ability to comply with scheduled visits, treatment plan, laboratory tests, and other study procedures	This criterion is not relevant in a real-world clinical setting.	N/A	N/A	N/A

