≥2 missed disease assessments	This criterion will not be operationalized.	Real-world progression is not evaluated at fixed intervals as was done in the trial. Patients with gaps in activity of greater than 90 days will be censored under the loss to follow-up definition.	The frequency of real-world progression assessments will be reported to contextualize study findings.

N/A = not applicable

7.4.4 Context and rationale for covariates (confounding variables and effect modifiers, e.g., risk factors, comorbidities, comedICATIONS)

Operational definitions for the study covariates are presented in [Table 9](#). Covariates were chosen based on the primary trial publication and the research team’s substantive knowledge of potential confounders. For time-varying characteristics, the value closest in time prior to study drug initiation will be used.

Table 9. Operational Definitions of Covariates

Characteristic	Details/Levels ^a	Type of variable	Assessment window
Patient Demographic Characteristics			
Age	Age at study drug initiation 18 to <65 yrs, ≥65 yrs	Continuous, Categorical	[Day -15]
Race	American Indian or Alaska Native, Asian, Native Hawaiian or other Pacific Islander, Black or African American, White, other or unknown race	Categorical	[Start of data, Day -15]
Ethnicity	Hispanic or Latino, not Hispanic or Latino, unknown	Categorical	[Start of data, Day -15]
Region	Northeast, south, midwest, west, missing	Categorical	[Start of data, Day -15]
Clinical Characteristics			
Oncology clinic site type	Academic, community, missing	Categorical	[Start of data, Day -15]
Performance status	ECOG performance status 0, 1, 2, or Karnofsky performance status 50, 60, 70, 80, 90, 100, or missing.	Categorical	[Day -105, Day -15]
Smoking status at initial diagnosis	Current smoker, former smoker, non-smoker, missing	Categorical	[Start of data, Initial diagnosis date]
Number of outpatient visits in past year	N/A	Continuous	[Day -380, Day -15]
Disease Characteristics and Treatment History			
Year of study treatment initiation	N/A	Categorical	[Day -15]
Prior therapy	Aromatase inhibitor, antiestrogen	Dichotomous	[Start of data, Day -15]
Disease stage at initial diagnosis	Disease stage I-IV	Categorical	[Initial diagnosis date - 30, Initial diagnosis date + 90]

Characteristic	Details/Levels ^a	Type of variable	Assessment window
Time between metastatic diagnosis and treatment initiation	N/A	Continuous	[Metastatic diagnosis date, Day -15]

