ECOG performance status assessment window	ECOG performance status for study inclusion will be assessed within 90 days from first study treatment initiation.	ECOG performance status for study inclusion will be assessed within 30 days from first study treatment initiation.	Shortening the assessment window for ECOG performance status may more accurately reflect patients' status at the time of study treatment initiation and will provide information on the sensitivity of results to this key inclusion criteria.	Assessing ECOG status closer in time to study treatment initiation may create a study population that is more similar to the trial population.	A larger number of patients may be missing ECOG performance status during the shorter time period. Patients with missing values will be included in the analysis in line with the primary approach.
Complete case - ECOG performance status	Patients with missing ECOG or Karnofsky performance status in the 90 days prior to first study treatment initiation are included.	Patients with missing ECOG or Karnofsky performance status in the 90 days prior to first study treatment initiation will be excluded.	Removing patients with missing ECOG performance status may reduce misclassification of disease severity and will enable descriptive comparison of the study population with and without these patients.	Excluding patients with missing ECOG may create a study population that is more similar to the trial population.	The sample size will be reduced.

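### As written, the 30-day ECOG sensitivity analysis cannot make the cohort more similar to the trial on documented performance status, because patients with no value in 30 days stay in

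*Combined protocol and SAP*

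**What the plan says.** All references are to the combined protocol and SAP.

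- **Primary rule (Section 7.3.2, Table 4).** Eligible values are "ECOG performance status 0-2 or missing Karnofsky performance status ≥50 or missing". The window is [Day -105, Day -15], explained as "Performance status will be evaluated in the 90 days before study drug initiation to balance missingness and misclassification". With several records, "For patients with multiple performance status records, the entry closest in time to study drug initiation will be used".
- **Sensitivity rule (Section 7.5.2, Table 11, row on the ECOG assessment window).** "ECOG performance status for study inclusion will be assessed within 30 days from first study treatment initiation". The limitations column expects more missing values and then says: "Patients with missing values will be included in the analysis in line with the primary approach".
- **Claimed strength (same row).** "Assessing ECOG status closer in time to study treatment initiation may create a study population that is more similar to the trial population". The rationale column gives a second aim, which is to show how sensitive the results are to this criterion.
- **Trial criterion (Section 7.1.1).** Eligible trial patients "had an Eastern Cooperative Oncology Group (ECOG) performance status of 0 to 2".
- **Covariate (Section 7.4.4, Table 9).** The performance status levels are "ECOG performance status 0, 1, 2, or Karnofsky performance status 50, 60, 70, 80, 90, 100, or missing", with the 90-day window.

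**The concern.** A shorter look-back makes a cohort more trial-like only if it removes patients whose recent status is unsuitable or unknown. Here, patients without a recent value are kept. A patient whose only record is 31-90 days old is reclassified as missing, and missing passes. If that record was out of range, the primary analysis excluded her and the sensitivity analysis lets her in.

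Two things are at stake. First, the row would be reported as having a property that its filter cannot give it. Second, the sensitivity cohort is the primary cohort plus a group that is probably small. A similar hazard ratio could then be read as robustness to better-timed performance status, when hardly anything about the cohort has changed.

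**Working it through.** **Inputs.** From Table 4: the 90-day window (105 - 15 = 90), the closest-entry rule, and missing values pass. From Table 11: a 30-day window, and missing values pass. Two assumptions are needed. The 30-day window looks backward as the primary one does, which by analogy is [Day -45, Day -15]. It applies to both scales. The plan gives no count for this row, so there is no figure to reproduce; the check concerns which patients can enter or leave.

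**Case by case, closest record before drug start**

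| Closest record | Primary (90 days) | Sensitivity (30 days) | Change |
|---|---|---|---|
| 0-30 days, in range | in | in | none |
| 0-30 days, out of range | out | out | none |
| 31-90 days, in range | in | in (as missing) | none |
| 31-90 days, out of range | out | in (as missing) | **added** |
| none within 90 days | in | in | none |

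Out of range means ECOG above 2 or Karnofsky below 50. A record within 30 days is also the closest within 90 days, so the first two rows cannot change.

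**Check by enumeration.** Each grid day holds no record, an in-range record or an out-of-range record.

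- ECOG alone, days 0, 10, 30, 31, 60, 90 and 120: 3^7 = 2,187 histories. An added history has nothing at days 0, 10 and 30, and its first record among days 31, 60 and 90 is out of range: 9 + 3 + 1 = 13 ways. Day 120 is free, so 13 × 3 = 39 are added. Removed: 0.
- Both scales pooled, closest record governs, days 10, 30, 31, 60 and 90: 3^10 = 59,049 histories. A day has 9 states, of which 5 include an out-of-range value. Added: 5 × 81 + 5 × 9 + 5 = 455. Removed: 0.
- Each scale must pass separately: each scale has 3^5 = 243 histories, of which 135 pass at 30 days and 122 at 90 days. Added: 135² - 122² = 18,225 - 14,884 = 3,341. Removed: 0. Here the out-of-range record is the latest one on at least one scale.

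Every added history has an out-of-range record 31-90 days before drug start. These counts show direction only; they are not patient frequencies.

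**Possible size, on assumed shares.** Section 7.9 gives 944 + 660 = 1,604 feasibility patients. Suppose 5% to 30% have their latest record at 31-90 days, and 1% to 10% of those are out of range.

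- Low: 1,604 × 0.05 × 0.01 = 0.8
- High: 1,604 × 0.30 × 0.10 = 48.1, or 3.0% of 1,604

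The shares are not in the documents. Section 7.9 also describes these patients as having no evidence of ECOG 2 or higher, so the base already leaves out the group in question. The range gives an order of magnitude and nothing more.

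**Covariate.** The Table 11 row changes the window for inclusion only. If the Table 9 window stays at 90 days, an added patient carries a value with no listed level. If it also moves to 30 days, she takes the missing level, and so do in-range patients whose latest record is 31-90 days old.

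**The case against.** The case for the plan has four parts.

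- **Other readings allow removals.** The row names only ECOG. If Karnofsky keeps 90 days, a patient with ECOG 1 at day 40 and Karnofsky 40 at day 60 is in the primary cohort and out of the sensitivity cohort. A rule that lets any ECOG entry in the window override Karnofsky also gives removals (1,768 added and 1,404 removed in the enumeration). This stands as a limit on the point. The second rule is not in the plan, which uses the closest entry. The first is an ambiguity that the row should settle.
- **Old records may be wrong.** A reader might infer that the added patients are known to be trial-ineligible, so that the cohort must move away from the trial. The documents do not support that. Status at drug start is unknown for these patients, some may have improved, and Table 4 presents the 90-day window as a compromise. The point holds on documented status only.
- **The second aim survives.** Asking whether exclusions based on older records affect the result is a fair robustness question. It would be too strong to say that the row is useless or that any result from it misleads. If the covariate window also moves, the weights change, and a difference from the primary need not come from the added patients.
- **A complete-case row already exists.** It does, in the next row of Table 11, but at 90 days. It does not test recency, so it does not repair this row.

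It is also true that the limitations column discloses that missing values are kept. It does not say that some of those patients have an out-of-range record in the primary window.

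**Conclusion.** The point holds in a limited form. With both scales' windows shortened together and the closest-entry rule kept, the primary cohort is contained in the 30-day cohort. The difference is the patients whose latest record is 31-90 days old and out of range. The strength stated in Table 11 therefore cannot arise on documented status, and near-agreement with the primary is largely built in, at least while the covariate window stays at 90 days.

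The number added is not in the documents and may be zero; the assumed shares give about 1 to 48. A reader might also infer that the added patients can never have a valid covariate value. That follows only if the Table 9 window stays at 90 days, which the row leaves unstated.

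The issue is confined to one of seven sensitivity rows and does not touch the primary estimate. The row should be changed, because as written it lacks a property it claims.

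**What to change.** In the Table 11 row on the ECOG assessment window:

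1. Require the closest record in the 30 days before drug start to be ECOG 0-2 or Karnofsky 50 or higher, and exclude patients with no record in those 30 days.
2. State that the 30-day window applies to both scales and to the performance status covariate in the propensity score model.
3. Replace the sentence that keeps patients with missing values.

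The resulting cohort lies inside the primary cohort. No separate 90-day exclusion is needed, because an in-range closest record within 30 days is also the closest within 90 days.

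The cost is one table row, one cohort filter and a smaller sample in this sensitivity analysis only. If that sample is too small, keep excluding patients whose closest 90-day record is out of range and delete the claimed strength. Under this fallback the cohort equals the primary cohort, so the row would test only the 30-day covariate, and the text should say so.
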